Clinical Significance: This study will demonstrate the supplemental motor relearning value of virtual reality/video games to CCFES therapy, (2) identify patients most likely to respond to both therapies, and (3) determine whether adding HTVG to CCFES simply enhances cortical activation underlying CCFES or engages additional cortical areas to improve response across broader ranges of severity and chronicity. This study is an important step toward the development and dissemination of new

treatments that may be applicable and effective across a wide range of patients who have lost hand function after stroke.

Specific Aims

AIM 1: Determine the effect of integrating Hand Therapy Video Games (HTVG) with Contralaterally Controlled Functional Electrical Stimulation (CCFES) on upper extremity motor outcomes

Hypothesis 1: Stroke patients treated with CCFES+HTVG will have greater and faster improvements in hand dexterity, upper limb impairment, and activity limitation than those treated with CCFES alone

AIM 2: Evaluate the effect of baseline impairment and time post-stroke on treatment response

Hypothesis 2: Compared to CCFES, CCFES+HTVG will benefit patients with greater baseline impairment and time elapsed post-stroke.

AIM 3: Explore the effects of CCFES+HTVG vs. CCFES on cortical activation during a hand task

Hypothesis 3: Compared to CCFES, CCFES+HTVG will exhibit greater re-mapping in the brain, demonstrated as greater lateralization of activity, greater recruitment of learning- based networks in ipsilesional and contralesional regions, and increased intensity of cortical activity.

Methods and Procedures

General Study Design

A single-blinded randomized controlled trial will be carried out to assess the effects of 12 weeks of CCFES+HTVG compared to CCFES. Dexterity, upper limb impairment, and activity limitation will be assessed at 0 (baseline), 3, 6, 9, 12 (end of treatment), 24, and 36 wks. Cortical activation (measured with fMRI) will be optionally assessed at 0 and 12 wks. The treatment dose will be the same for both groups: 10 sessions per week (7.5 hrs) of self-administered treatment at home plus 2 sessions per week (3 hrs) of group-specific occupational therapy in the lab.

Device

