For the CCFES group, during each of three 15-min periods, audio cues issued from the stimulator will prompt the subject to attempt to fully open both hands for several seconds, then relax both hands for several seconds, and repeat the cycle. Stimulation will open the paretic hand when the subject opens the contralateral unimpaired hand. The subjects will be instructed to attempt to exert effort to open the paretic hand at the same time they open their non-paretic hand. As in our previous studies, the cue durations will be adjusted every 2 weeks, starting at 6 sec open/14 sec relax (30% duty cycle),

then changing to 8 sec open/12 sec relax (40% duty cycle), and finally 10 sec/10 sec (50% duty cycle). These duty cycles are within the 20% to 50% range of duty cycles used in other NMES studies.⁸⁻¹² The purpose of the graded duty cycle is to prevent fatigue early in the intervention and to progressively build greater strength with longer duration muscle contractions.¹⁰ A 3-minute rest will follow each 15-minute period.

For the CCFES+HTVG group, during each of three 15-minute periods, the subject will play one of the 4 previously described games, switching to another game every 15 minutes with a 3-minute break between games. The subjects will use the CCFES system to assist hand opening and will be instructed to exert effort to open the paretic hand at the same time they open their non-paretic hand while playing the games. Because games will be introduced and taught one at a time over the first 4 weeks, during the first two weeks of treatment, the subject will have only learned to play one or two games and therefore will repeat the same game over multiple 15-min periods within a single session. More games will be added (unlocked) as the subject learns them in the lab. The therapist will unlock games and set the difficulty settings for each game at the lab sessions. These settings will be stored on a USB key, which the subject must plug into the home computer in order to play the games at home.

Therapist-Administered Lab Sessions

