Lab sessions will last ~1.5 hrs. During the first 20 minutes, the CCFES group will do the repetitive CCFES-mediated hand opening exercise, with the therapist reinforcing instructions to open both hands at the same time in response to the cues. The CCFES+HTVG group will play several minutes of each of the video games they were assigned to do at home, while the therapist adjusts the difficulty levels of the games and/or introduces and teaches a new game. Then, for both groups, for 60 minutes the therapist will instruct and encourage subjects to perform functional tasks with the paretic arm and hand, using CCFES to assist hand opening during task practice. Tasks will involve hand opening and closing to pick up, manipulate, and release objects commonly used in daily life. Task difficulty will progress from easy-to-acquire-and-manipulate to tasks requiring wider hand opening, greater skill, graded hand opening (controlled release), and coordination of hand function with proximal upper limb movement.

Data Collection

Baseline Variables

A clinical coordinator will collect baseline characteristics from the participants' electronic medical record(s) and by interview. Data collected will include demographic (e.g., sex, age, race, pre-morbid hand dominance), stroke-related (e.g., time post-stroke, hemorrhagic or ischemic, cortical or subcortical, right or left, Stroke Impact Scale score), and neurologic data (e.g., side of hemiparesis, cognition, neglect, visual deficits, aphasia), as well as co-morbidities, medications, and cognitive function (Montreal Cognitive Assessment). The balance of these variables between the two groups and their effect on the outcomes will be evaluated.

Adherence

Adherence to the home regimen will be monitored with electronic data logging and participant diaries. The stimulator logs the number of cued hand opening exercise periods completed (CCFES group) and the number of CCFES-mediated hand opening/closing repetitions (both groups). The HTVG system logs game setup/difficulty settings, game performance data (e.g., scores), and number of paretic hand opening/closing repetitions. Participants will also be given a paper diary to log completion of sessions. The diaries will be reconciled with electronic data logs at every lab session, in the presence of the participant to encourage adherence.

Concomitant Therapies

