- Electrical stimulation should not be used by patients with implanted electronic devices (cardiac demand pacemakers etc.) unless under specialized medical supervision.
- Do not participate in this study if you have a history of potentially fatal cardiac arrhythmias.
- Electrical stimulation should not be used by people who have poorly controlled epilepsy.
- The stimulator has been programmed specifically for the intended user only. Do not let others use the stimulator.

Statistical Analysis Plan

We hypothesize that the CCFES+HTVG group will have greater post-treatment gains than the CCFES group on upper extremity motor outcomes. Exploratory looks at the data will be done before fitting our models. The adaptive randomization should force relatively good balance of potential confounding variables (e.g., fMRI eligible, severity of impairment, time post-stroke), but imbalances in treatment adherence or any other baseline covariate (e.g., lesion location, etc.) or adherence may still require their inclusion as covariates. Each measure will be modeled using a linear mixed effects approach which is well-suited for handling correlated repeated measurements, unbalanced data, and missing data and dropouts in longitudinal studies, while permitting us to control for potential confounders.¹ Least square (LS) means will be calculated using model estimates and adjusted for missing values for each group at each time point. This approach allows comparisons and estimates of treatment group effects at any time point, and also allows comparisons and estimates across time points within groups to evaluate the persistence or decay of the treatment effect. Secondarily, we hypothesized that participants who were less than 2 years after stroke or had moderate hand impairment at baseline would improve more than participants who were more than 2 years after stroke or had severe hand impairment at baseline. A mixed effects modeling analysis will be used similar to the primary analysis to evaluate the effects of time post-stroke and impairment severity. For fMRI data, differences from baseline to EOT in beta coefficient maps for each region of interest will be evaluated with paired t-tests and cluster threshold set to >100 voxels. Between-group comparisons will be made with independent t-tests.

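### The SAP treats adherence, which is recorded after randomisation, like a baseline covariate and lets an arm imbalance bring it into the efficacy models, including the primary Box and Blocks Test

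*Combined protocol and SAP*

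**What the plan says.** The covariate rule is in the Statistical Analysis Plan. After noting that adaptive randomisation should balance the main confounders, it adds that "imbalances in treatment adherence or any other baseline covariate (e.g., lesion location, etc.) or adherence may still require their inclusion as covariates". The next sentence gives its reach: "Each measure will be modeled using a linear mixed effects approach". Under Upper Limb Motor Assessments the BBT is marked as primary, so the rule covers the primary outcome. The SAP also says that the data will be explored before the models are fitted. It gives no imbalance threshold, names no adherence measure, and does not designate an adherence-free model as primary.

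The question is a comparison of assigned groups. Aim 1 is to "Determine the effect of integrating Hand Therapy Video Games (HTVG) with Contralaterally Controlled Functional Electrical Stimulation (CCFES) on upper extremity motor outcomes", and the SAP hypothesis is that the "CCFES+HTVG group will have greater post-treatment gains than the CCFES group on upper extremity motor outcomes".

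The Adherence section shows when and how adherence is recorded: "Adherence to the home regimen will be monitored with electronic data logging and participant diaries". Paper diaries of completed sessions are kept in both arms and reconciled with the electronic logs at lab sessions. What the device itself records is not the same in the two arms. Its memory holds "the number of cued hand opening exercise periods completed (CCFES group) and the number of CCFES-mediated hand opening/closing repetitions (both groups".

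The Concomitant Therapies section has a related rule: any group imbalance in such therapies is to be accounted for in the analysis. It does not distinguish therapy in use before randomisation from therapy started afterwards.

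**The concern.** Adherence to the home regimen arises after assignment, so it may be a consequence of assignment. What participants do at home is the randomised contrast. The CCFES arm follows timed cues. In the CCFES+HTVG arm, "during each of three 15-minute periods, the subject will play one of the 4 previously described games". Games could make people practise more, or less.

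If adherence lies on the path from assignment to recovery, adjusting for it removes part of the effect that Aim 1 sets out to estimate. If adherence and recovery share unmeasured causes, such as motivation, adjusting for it once it differs by arm adds bias even when the treatment has no effect. Neither problem arises with a covariate measured before randomisation.

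The choice is also left until the data have been seen, with no threshold and no named measure. At stake is whether the reported BBT difference still estimates the comparison of CCFES+HTVG with CCFES as assigned.

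**Working it through.** **1. Plan figure to reproduce.** There is none. The documents give no alpha, power, effect size, SD or expected adherence difference. The one design input is the planned maximum of 52 participants, taken here as 26 per arm (an assumption, since no allocation ratio is stated).

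**2. Why the trigger matters.** In a linear model with one outcome,

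adjusted arm estimate = unadjusted arm difference − (arm difference in adherence × within-arm slope of outcome on adherence).

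If assignment does not affect adherence, the second term is zero on average and there is no bias. If it does, the estimate moves. With a positive slope it shrinks when CCFES+HTVG raises adherence and grows when it lowers it; with a negative slope these directions reverse.

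**3. The measure itself can create an imbalance.** Completed cued periods are logged only in the CCFES arm; the stimulator count listed for both arms is opening/closing repetitions. In the CCFES arm the cues run "starting at 6 sec open/14 sec relax (30% duty cycle", then 8/12 and 10/10 seconds. Each cycle is 6 + 14 = 8 + 12 = 10 + 10 = 20 seconds, so a 15-minute period has 900 / 20 = 45 cues and a session has 3 × 45 = 135. In the game arm the count depends on play, and no rate is given. On this measure the arms could differ even if every session were completed.

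**4. Illustration with a true effect.** Assumptions: two-sided 0.05; one end-of-treatment outcome fitted by least squares, standing in for the mixed model; within-arm SD 1 for adherence and outcome; true total effect 0.80 SD; within-arm slope 0.50; 40,000 simulated trials per setting. Unadjusted, the estimate is 0.80 SD with 81% power. Rule (a) adjusts only when the adherence difference has p<0.05. Rule (b) always adjusts, and its expected estimate is 0.80 − 0.50 × shift. The SAP states neither rule.

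| Adherence shift (SD) | (a) estimate | (a) power | (b) estimate | (b) power |
|---|---|---|---|---|
| +0.3 | 0.74 | 76% | 0.65 | 74% |
| +0.5 | 0.64 | 65% | 0.55 | 58% |
| +0.8 | 0.44 | 36% | 0.40 | 32% |
| −0.5 | 0.96 | not shown | 1.05 | not shown |

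The movement in the estimate is proportional to the slope. With slope 0.20 it is 0.20/0.50 = 0.4 times as large. Rule (a) then gives 0.80 − 0.4 × 0.06 = 0.78, 0.80 − 0.4 × 0.16 = 0.74 and 0.80 − 0.4 × 0.36 = 0.66 SD at the three positive shifts. With slope −0.50 the estimate rises by the same amounts: 0.86, 0.96 and 1.16 SD.

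**5. Illustration with no true effect.** Here adherence and outcome are correlated only through an unmeasured common cause. Two-sided type I error under rule (a):

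| Correlation | Shift 0.3 | Shift 0.5 | Shift 0.8 |
|---|---|---|---|
| 0.16 | about 5% | 5% | 7% |
| 0.25 | about 5% | 6% | 9% |
| 0.36 | about 5% | 7% | 15% |
| 0.50 | about 5% | 9% | 27% |

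Under rule (b) with correlation 0.50 the figures are 9%, 16% and 32%. The expected estimate under rule (b) is −correlation × shift, for example −0.50 × 0.8 = −0.40 SD; under rule (a) it is −0.36 SD in that setting. With these positive shifts the excess rejections therefore go against CCFES+HTVG. If CCFES+HTVG lowered adherence, the sign would reverse and they would favour it.

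**6. A second set of assumptions.** Take a direct effect of 0.50 SD, an adherence effect of 0.3 on outcome, and a common cause acting at 0.5 on each. A 0.5 SD adherence shift turns a true total effect of 0.65 into an adjusted 0.37; a 1.0 SD shift turns 0.80 into 0.25. In every setting tried, leaving adherence out recovered the true total effect.

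**The case against.** The strongest reply is that the sentence gives a permission, not a plan. It says imbalances may require adjustment, and it is visibly garbled, naming adherence twice, so the grouping with baseline covariates may be a drafting slip. Nothing in the documents shows that adherence will differ by arm, relate to outcome or be used. This stands as a limit on the claim: a biased BBT result is not certain. It does not rescue the sentence, which leaves the option open for the primary model.

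Second, the design prescribes equal doses, and the value of games at equal achieved practice is a sensible question. That is fair as a secondary aim. It needs its own target and an assumption of no unmeasured common causes, and it is not the comparison stated in Aim 1 or the SAP hypothesis. Equal prescription does not make achieved adherence a baseline variable.

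Third, the SAP never chooses repetitions as its adherence measure, and reconciled diaries offer a session count in both arms. This also stands: the repetition arithmetic shows what one permitted choice could do, and the main point does not depend on it.

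Fourth, the sizes rest on assumed slopes. With slope 0.20 the loss is much smaller, and at a 0.3 SD shift under the p<0.05 rule type I error stays near 5%.

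Finally, limiting adjustment to named variables goes further than deleting adherence. That is so, but lesion location or any other baseline variable of interest can simply be named in advance.

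**Conclusion.** The concern holds: the covariate sentence is wrong as written and should be fixed. Adherence is measured after randomisation, is worded together with baseline covariates, and may enter the BBT model on the strength of an arm imbalance, which is the circumstance in which adjustment distorts the randomised comparison. Confidence in that is high, because it rests on the text alone.

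The harm is conditional on three things together: an arm difference in adherence, a relation of adherence to outcome, and use of the permission. Under the assumptions above it ranges from slight (0.78 for a true 0.80 SD, at slope 0.20 and shift 0.3 under the p<0.05 rule) to a halving of the estimate (0.40, at slope 0.50 and shift 0.8 with adjustment always applied). It can also run upward. No row is offered as typical or as a limit.

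The concomitant-therapy rule is a secondary instance of the same fault, since it does not separate use before randomisation from use started later.

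**What to change.** In the Statistical Analysis Plan, remove adherence from the covariate sentence. State that the BBT model and the other efficacy models compare participants by assigned arm and adjust only for named variables measured before randomisation, such as the baseline score and the four adaptive-randomisation factors in the Randomization section. If lesion location or another baseline variable is wanted, name it there.

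In Concomitant Therapies, limit covariate adjustment in these models to therapy in use before randomisation. Current upper-limb rehabilitation and botulinum toxin within 3 months of enrolling are already excluded, so this leaves mainly splints, slings, spasticity medication and any earlier toxin injections.

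Report adherence, with its measure named, and later concomitant therapy descriptively by arm. An adherence-adjusted analysis may be kept if it is labelled exploratory and states its target, its adherence measure and its assumption of no unmeasured common causes.

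The cost is two reworded sentences and a decision on the covariate list and adherence measure. No new data or participants are needed, and the exploratory analysis is optional.

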For each participant, a stimulator will be set up to stimulate finger and thumb extension in response to input from the CCFES glove. Up to 3 channels of stimulation will be used. Surface electrodes will be positioned on the forearm to activate the extensor digitorum communis (EDC) and extensor pollicis longus (EPL). Abductor pollicis brevis (AbPB), dorsal interossei (DI), or extensor indicis proprius (EIP) may also be stimulated if they are necessary to achieve functional hand opening. A maximum

stimulation intensity will be determined for each electrode, defined as the pulse width that produces maximum finger or thumb extension without discomfort. These pulse widths will be entered into a program that is then downloaded to the stimulator, ensuring that the stimulator used by each participant is customized to them.

Participant Education

After customizing the stimulator, the treating therapist will instruct and train the participants, and their caregivers if necessary, how to put on the components (i.e., electrodes, glove, and bend sensor for game play if applicable). The electrodes will be outlined on the skin and photographs of the electrodes correctly positioned will assist the subject in placing them correctly at home. An instruction manual will be reviewed with every participant, and each will be trained to operate the stimulator and HTVG (if applicable). The treating therapist will make home visits if needed to troubleshoot any problems the subjects may be having at home.

Study Treatments

The treatment regimens for both groups will last 12 weeks and consist of: a) 10 self-administered sessions per week at home, and b) 20 therapist-guided sessions in the FES Center at the LSVDVAMC (2 per week except on weeks that include an assessment visit).

Self-Administered Home Sessions

The 10 home sessions per week will be distributed so that no more than 2 sessions are done per day (separated by >2 hours), and no more than one session per day on days in which a lab session is scheduled.

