We will enroll only patients who are no longer receiving rehabilitation therapies to the upper limbs. The use of electrical stimulation or other experimental rehabilitation techniques involving the hemiparetic upper limb, changes in spasticity medications, botulinum toxin injections to upper limb muscles, use of an arm sling, and use of a resting hand splint will be discouraged unless it is deemed medically necessary. To account for the potential confounding effect of such concomitant therapies, all concomitant therapies will be documented and any group imbalance will be accounted for in the statistical analysis.

Upper Limb Motor Assessments

All subjects will undergo assessments of hand dexterity (BBT), upper limb impairment (UEFM, Maximum Voluntary Finger and Elbow Extension and Tracking), activity limitation (AMAT) by a blinded assessor at 0 (baseline), 3, 6, 9, 12 (end of treatment), 24, and 36 wks. All assessments will be done with no electrical stimulation. Subjects will refrain from using their stimulators for 24 hours prior to their 3, 6, 9, and 12 week assessments in order to avoid any transient carry-over effect or muscle fatigue.

Box and Blocks Test (primary)

The BBT is a measure of gross manual dexterity, which requires the subject to pick up one block at a time, move it over a partition, and release it in a target area as many times as possible in a 60-sec period.

Upper Extremity Fugl-Meyer Assessment

The UEFM is a measure of post-stroke upper limb motor impairment. The assessor requests the subject to attempt specific volitional movement of the upper limb (shoulder, elbow, forearm, wrist, and hand), and rates their ability to perform each movement using a 3-point ordinal scale (0, cannot perform; 1, perform partially; and 2, perform fully). The maximum score is 66.

Arm Motor Abilities Test

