The WRAT4 (Wide Range Achievement Test 4) will be administered to all non-aphasic Candidates at the baseline visit for use in correlation data analysis. All aphasic Subjects will be administered the PPVT III (Peabody Picture Vocabulary Test) instead of the WRAT4 at baseline (0) weeks of the study at MetroHealth Medical Center for use in correlation data analysis. The WRAT4 is a verbal assessment whereas the PPVT III is a non-verbal assessment. This will allow us to gather baseline cognitive information from both our verbal and non-verbal Candidates. The subjects' impressions of the effectiveness of the intervention, the dose, and the ease of using the device/equipment, and their degree of engagement with the home sessions will be captured with questionnaires. The purpose is to gain insight into how well the device and dosage are tolerated and the subjects' perception of effectiveness. One questionnaire will be administered at all outcomes assessment visits by the blinded assessor and two others at end of treatment by a non-blinded staff member who will have no other interaction with the subjects.

Tower Test (Optional; PI Discretion)

The Tower Test is a well-known test of executive function (Shallice, 1982; Keith-Berg 2002), specifically used to detect deficits in planning. The test consists of a board with pegs and several beads with different colors. The examiner uses the beads and pegs to present the examinee with problem-solving tasks that require the examinee to move beads of different sizes and colors to the three pegs in order to match a series of configurations presented by the examiner. The performance of the examinee is compared to representative samples of individuals of the same age to derive hypotheses about the person's executive cognitive ability. The test would be administered before and after the treatment phase and at 6 months post-treatment.

fMRI Assessment

fMRI Procedure and Equipment

We will utilize blood oxygenation level-dependent (BOLD) fMRI to reveal cortical regions that are active during a motor task performed with each hand in turn. Based on our previous work,¹⁸ we will use a tracking task where patients open and close their fingers to move a cursor up and down to trace a 0.4 Hz sine wave scrolling horizontally across a screen. A mirror mounted to the head coil will allow

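### The SAP allows treatment adherence, which arises after randomization, into the primary BBT model as if it were a baseline confounder

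*Combined protocol and SAP*

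**What the plan says.** The Statistical Analysis Plan expects the adaptive randomization to balance the main prognostic factors, then adds that "imbalances in treatment adherence or any other baseline covariate (e.g., lesion location, etc.) or adherence may still require their inclusion as covariates". Adherence is named twice and is worded as one of the baseline covariates. The next sentence fixes the scope: "Each measure will be modeled using a linear mixed effects approach". The BBT is labelled primary under Upper Limb Motor Assessments, so the clause reaches the primary model. The stated purpose of the covariates is control of confounding.

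Adherence is collected during the 12-week home regimen. Under Adherence: "The diaries will be reconciled with electronic data logs at every lab session, in the presence of the participant to encourage adherence". The Questionnaires section treats interest in the home sessions as something to be measured as well: participants' views are sought, and "their degree of engagement with the home sessions will be captured with questionnaires".

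Under Concomitant Therapies, the protocol says that "all concomitant therapies will be documented and any group imbalance will be accounted for in the statistical analysis".

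The documents give no estimand, no intention-to-treat statement, no definition of adherence for analysis and no threshold for imbalance. Nothing says that adherence-adjusted models are sensitivity analyses only. The SAP does not say whether baseline BBT is a response or a covariate, or whether covariates interact with visit.

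**The concern.** Aim 1 asks what integrating video games with CCFES does to motor outcomes. The arms are randomized and have the same prescribed dose, so comparing them as assigned answers that question. The arms differ mainly in the home sessions (game play or cued exercise), and these are what adherence measures. If games lead people to practise more, and practice raises BBT, that route is part of the package effect, and adjusting for adherence removes it. If the game arm adheres less, adjustment moves the estimate in favour of games.

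A second problem arises if an unmeasured trait such as motivation or hand ability drives both adherence and gain. The adjusted contrast is then biased even as an answer to the equal-adherence question.

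The trigger adds to the difficulty. An observed imbalance is what prompts adjustment, and imbalance is more likely when the arm affects adherence, which is the case where adjustment misleads.

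**Working it through.** **Inputs from the documents.** Up to 52 participants, taken as 26 per arm (1:1 allocation is assumed). Home sessions: 10 × 12 = 120, or 12 × 7.5 h = 90 h. Lab sessions: 20 × about 1.5 h = 30 h. The home component is 90/(90 + 30) = 75% of prescribed time. The plan states no power, effect size or SD, so it has no figure to reproduce.

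**Assumed inputs.** True package effect τ = 0.80 SD of BBT change, which gives about 81% power unadjusted at two-sided 0.05. d = arm difference in sessions completed ÷ within-arm SD (for example 10 percentage points with SD 20 gives d = 0.5). r = within-arm correlation of sessions with gain.

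**Step 1: shift in a one-visit model of change.** Let adherence A = z + d·arm and gain = τ·arm + r·z + √(1 − r²)·e. Substituting z = A − d·arm gives gain = (τ − r·d)·arm + r·A + √(1 − r²)·e. The coefficient on arm after adjustment is therefore τ − r·d.

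- d = 0: no shift for any r; type I error stays at about 5%.
- d = 0.5, r = 0.25: shift 0.25 × 0.5 = 0.125 SD, so 0.80 is estimated as 0.675.
- d = −0.5, r = 0.25: the same shift upward, to 0.925.

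**Step 2: operating characteristics by simulation** (20,000 trials per cell, game arm adhering more; type I error is rejection when the true package effect is zero):

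| d, r | Rule | Mean shift (SD) | Power | Type I error |
|---|---|---|---|---|
| any | never adjust | 0 | 81% | 5% |
| 0.5, 0.1 | always adjust | 0.05 | 72% | 5% |
| 0.5, 0.25 | always adjust | 0.13 | 66% | 7% |
| 0.5, 0.25 | adjust if imbalance p<0.05 | 0.08 | 71% | 6% |
| 1.0, 0.25 | always adjust | 0.25 | 43% | 13% |

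The p<0.05 trigger is also an assumption. The SAP names none.

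**Step 3: model form.** The SAP's model covers repeated visits, with BBT also measured at week 0. Suppose baseline BBT is one of the responses and adherence enters only as a main effect, γA. The same γA is then added at baseline and at every later visit, so it cancels from the difference in gain, and the shift is about 0. With an adherence-by-visit term, or with baseline BBT as a covariate, the full r × d returns (simulated at d = 1, r = 0.25: −0.25 SD of change in both). The cancellation applies only to gain. The SAP also plans group comparisons at individual time points, and those still shift under the main-effect form if adherence correlates with baseline ability.

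**Step 4: unmeasured common cause.** Let a be the arm difference in adherence (SD), b the causal effect of adherence on gain, and c the association due to a shared cause. The adjusted coefficient is total − a(b + c). With total = 0.80, a = 0.5, b = 0 and c = 0.20, it is 0.80 − 0.5 × 0.20 = 0.70. Adherence here has no causal effect, so the equal-adherence effect is also 0.80. The adjusted estimate is wrong for both questions.

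**The case against.** The strongest reply is that harm is possible but not shown. The SAP says only that adjustment may be required. Perhaps the plainest reading of its model, with week 0 among the repeated measures and covariates as main effects, leaves the gain contrast essentially unchanged. This stands. A reader might infer that the primary result will be biased, or that the larger figures above are expected. The documents support neither, since they give no adherence SD, arm difference or correlation with gain. What remains is that the SAP does not commit to the harmless form and also plans comparisons at individual time points.

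A second reply is that equal prescribed doses point to a dose-matched question. That reading is possible but is not stated as the aim, and covariate adjustment answers it only if adherence and gain share no unmeasured cause. A labelled supplementary analysis can still report it.

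A third concerns concomitant therapies. A reader might infer that the protocol commits the primary model to adjusting for therapy received after randomization. It does not: its sentence names neither the primary model nor covariate adjustment, and a supplementary analysis would satisfy it. It also covers use that may predate enrolment, such as a sling or resting splint, for which adjustment is valid. That sentence needs clarifying; it is not a second instance of the same error.

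Adjustment for true baseline covariates such as lesion location is not in question.

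**Conclusion.** The concern holds as a stated rule that can give the wrong primary contrast. Adherence arises after assignment, may respond to the arm, and is admitted to the primary BBT model on the same footing as a baseline confounder.

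The size is undetermined. It is zero if adherence does not differ by arm, about zero for the gain contrast under the main-effect form with baseline as a response, and r × d otherwise. The moderate illustration (d = 0.5, r = 0.25) costs 10 points of power with a p<0.05 trigger and 15 points if adherence is always adjusted for. All values of d, r, τ and the trigger are assumptions. The conclusion also rests on reading Aim 1 as the effect of the package as assigned, which is natural for a randomized comparison but is not written as an estimand.

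**What to change.** 1. **Statistical Analysis Plan.** Delete adherence from the covariate clause. State: *No variable measured after randomization enters the primary BBT model. Baseline covariates may be used if they are named before outcome data by group are examined.*
2. **Concomitant Therapies.** State that therapies begun or changed after randomization will be reported by group and examined only in a labelled supplementary analysis. Use already present at baseline may be treated as a baseline covariate.
3. **Adherence.** Report adherence by arm as reconciled home sessions completed, out of 120. Label any adherence-adjusted BBT analysis as supplementary; it does not replace the primary estimate.

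The cost is a few sentences in three sections and one table from data already collected, with no new visits or measurements. The downside is a small loss of power if adherence is unrelated to arm and adjustment would have been made: about 5 points at r = 0.4 (86% adjusted against 81% unadjusted).
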